#### 4.4.1.3. Suspected Adverse Reaction

An AE will be counted as a *suspected adverse reaction* (SAR) if the Clinical Investigator selected either of the two options on the AE eCRF listed in Section 4.4.1.3.1 and Section 4.4.1.3.2.

##### 4.4.1.3.1. Study-Medication Related Adverse Event

- “Related” under Item 11 (Relation to Study Drug)

##### 4.4.1.3.2. Injection-Procedure Related Adverse Event

- “Related to the injection procedure” under Item 12 (Attributable Causes)

#### 4.4.1.4. Events of Special Interest

*Events of Special Interest* (ESIs) in this study include study drug administration error and Pregnancy.

#### 4.4.2. Other Safety Assessments

All the other safety measures besides AE to be evaluated for the SPRING study are listed in Table 3.

**Table 3 Other Safety Assessments**

Safety Measures	Note
Slit-lamp Biomicroscopy: Vitreous haze	VH is assessed for each eye using the modified SUN scale as 0, 0.5+, 1+, 1.5+, 2+, 3+, or 4+. A decrease in VH score

	indicates improvement in the vitreous inflammation.
Best-corrected visual acuity	BCVA measures the acuteness or clearness of best-corrected vision in ETDRS letters (e.g., 75 letters). An increase in BCVA indicates improvement in the best-corrected vision. A 5-letter difference in visual acuity is equivalent to one Snellen line. A BCVA score of 85 ETDRS letters is equivalent to 20/20 vision, which is considered normal vision.
Intraocular pressure (IOP)	IOP, the fluid pressure inside the eye, is recorded in mmHg with one decimal point (e.g., 24.0 mmHg). If DE-109 is administered, a second assessment of IOP is made after injection.
Indirect ophthalmoscopy: lens and cataract	The lens of an eye is classified as Phakic, Aphakic, or Pseudophakic. Phakic lens is assessed for the presence of cataract (Yes or No).
Indirect ophthalmoscopy: Retina, macula, choroid, optic nerve	Retina, macula, choroid, and optic nerve, if able to be assessed, are graded as Normal or Abnormal. If DE-109 is administered, these ophthalmoscopy parameters are performed again after injection.
Slit-lamp biomicroscopy a : Lid Hyperemia, Lid Edema, Conjunctival Hyperemia, Chemosis, Corneal Edema, Conjunctival Discharge Exudate, Anterior Chamber Flare	The status of each of these biomicroscopy parameters is rated as 0 = None, 1 = Mild, 2 = Moderate, or 3 = Severe. For each abnormal record, the clinical significance (Clinically Significant or Not Clinically Significant) is also determined.
Slit-lamp biomicroscopy a : Pupil, Lashes, Ocular Motility, Iris	The status of each of these biomicroscopy parameters is determined as Normal or Abnormal. For each abnormal record, the clinical significance (Clinically Significant or Not Clinically Significant) is also determined.
Slit-lamp biomicroscopy a : Vitreous Cell Count	This measure is rated as 0 = 0 cells, 0.5+ = 1-10 cells, 1+ = 11-20 cells, 2+ = 21-30 cells, 3+ = 31-100 cells, or 4+ = $\geq 100$ cells.
Slit-lamp biomicroscopy a : Anterior Chamber Cell	This measure is rated as 0 = <1 cell, 0.5+ = 1-5 cells, 1+ = 6-15 cells, 2+ = 16-25 cells, 3+ = 26-50 cells, or 4+ = $\geq 50$ cells.
Central retinal thickness	At investigator's discretion, assessments of both eyes by OCT

(CRT) a	imaging methods are performed. Measurement of CRT in microns is obtained from the OCT reading. Equipment type is specified. Images are collected into a central repository
--------------------	--

a For subjects under US Amendment 01 only.

## 4.5. Other Definitions

### 4.5.1. Rescue Therapy and Rescue Rate

*Rescue therapy* refers to any treatment that would have a therapeutic effect on the uveitis in the posterior segment (e.g., systemic treatment with an immunosuppressant agent, or a corticosteroid injection in the study eye) other than intravitreal DE-109. Topical ocular corticosteroid medication is not considered rescue therapy. Data related to rescue therapies will be reviewed and documented by the Medical Monitor prior to database lock to make the final determination of whether a medication will be classified as rescue therapy. *Rescue rate* is defined as the percentage of subjects who receive rescue therapy during the SPRING study among all subjects.

### 4.5.2. Prior and Concomitant Medications

*Prior medications* are non-study medications started and ended prior to the enrollment (Day 1) of the study. *Concomitant medications* are non-study medication taken during the study, i.e., the treatment period of a concomitant medication taken by a subject needs to overlap with the observation period from Day 1 to the Study Exit of the subject.

All medications are coded using the World Health Organization Drug Dictionary Enhanced (WHO-DDE) March 2014 version. Each medication will be classified using the Anatomical-Therapeutic-Chemical (ATC) classification system and mapped to a WHO-DDE preferred drug name.

## 5. STUDY POPULATION

### 5.1. Safety Population

*Safety Population* will include all enrolled subjects with any safety assessment data (defined in Section 4.4) collected during the SPRING study, regardless of receiving an injection of DE-109 (440 µg) or not in this study. It will be the analysis population for descriptive summaries of all safety measures.

## 6. GENERAL CONSIDERATIONS

All variables will be summarized by the last dose received in SAKURA study and overall. Continuous variables will be summarized using descriptive statistics such as number of observations (n), mean, standard deviation, medium, minimum, and maximum. Categorical variables will be tabulated using frequency (n) and percent (%).

All data manipulations and descriptive summaries will be performed using SAS Version 9.4 or later.

## 6.1. Adjustments for covariates

No inferential analysis is planned for this study. Therefore, no covariate will be adjusted.

## 6.2. Handling of Missing Data

### 6.2.1. Safety Measures

Descriptive summaries of safety measures will be based on observed data only. No imputation of missing scores will be implemented.

### 6.2.2. Dates for Medical Events and Medications

Completely or partially missing onset and resolution dates for medical events including medical history and AEs will be imputed in a conservative fashion as in Table 4.

**Table 4 Handling of Missing Date**

Date	Type of Missing Date	Handling of Missing Date
Event onset date (e.g., YYYY-MM-DD)	Completely missing	No imputation will be applied.
	Only YYYY is available	Use the first day of YYYY to impute the missing month and date parts of the onset date
	YYYY and MM are available but DD is missing	Use the first day of MM to impute the missing date part of the onset date
Event resolution date (e.g., YYYY-MM-DD)	Completely missing	No imputation will be applied. The event will be considered ongoing (i.e., not resolved) at the last visit date.
	Only YYYY is available	Use the last day of YYYY to impute the missing month and date parts of the resolution date
	YYYY and MM are available but DD is missing	Use the last day of MM to impute the missing date part of the resolution date

The same rules will be followed to impute completely or partially missing start and end dates of concomitant medications.

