### **14.4. Handling of Missing Values**

For safety measures, missing scores will not be imputed for data summaries.

Completely or partially missing onset and resolution dates for AEs and completely or partially missing start and end dates of concomitant medications will be imputed in a conservative fashion that will be detailed in the SAP.

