## 4.4. Safety Related Definitions

### 4.4.1. Adverse Event

Under Protocol 32-009, an AE is defined as any *on-study* untoward medical occurrence (e.g. sign, symptom, disease, syndrome, intercurrent illness) that occurs in a study subject, regardless of the suspected cause and regardless of timing of DE-109 (440 µg) administration. An on-study AE can occur any time after the date of informed consent through the last study visit. An AE will be considered as *treatment-emergent* if the AE occurred on or after the date of the first DE-109 (440 µg) treatment in Spring Study up to the last study visit. Treatment-emergent AEs are a subset of on-study AEs.

The severity of each AE will be graded by the Clinical Investigator as Mild (aware or unaware of event, but easily tolerated), Moderate (discomfort enough to cause interference with usual activity), or Severe (incapacitating; unable to work or perform usual activity). Each AE will be classified into a system organ classification (SOC) and coded to a preferred term using Medical Dictionary for Regulatory Activities (MedDRA 16.0).

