#### **8.1. Adverse Event**

All AE(s) will be coded by MedDRA 16.0, 2013. All analysis will focus on on-study AEs given the PRN nature of this study. The information that whether an AE is treatment emergent or not

will be provided in all the AE related listings. All AE tables will be summarized by last dose received in SAKURA study, received injection or not in SPRING study, and overall.

Besides the overall summary of AEs, subjects with any AE(s) will be tabulated by SOC, preferred term, and maximum severity. A subject who experienced multiple AEs within a SOC or preferred term will be counted only once for that SOC or preferred term. SAEs, SARs, Serious SARs, study-medication related AEs, and injection-procedure related AEs will be tabulated similarly.

Ocular AEs, ocular SARs, serious ocular AEs, and serious ocular SARs will be summarized. Any ocular AE that occurred simultaneously to both eyes will be counted once for both the study eye and the fellow eye.

Sight-threatening AEs will be summarized by type of event specified in [Section 4.4.1.2.1](#).

Eye disorders AEs may be tabulated using lowest level term and preferred term to provide more detailed information.

Non-ocular AEs and serious non ocular AEs will be presented by SOC and preferred term.

All AEs reported during the study will be listed. SAEs, SARs, Ocular AEs, study-medication related AEs, injection-procedure related AEs, AEs leading to death, AEs leading to discontinuation, sight-threatening AEs, and ESIs, if any, will be listed separately.

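### SAP Table 4 back-dates partial AE onsets without checking the first SPRING injection, so the treatment-emergent flag in the AE listings can be lost but, within the recording window, never wrongly gained

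*SAP*

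**What the plan says.** Protocol 14.4 leaves the detail to the SAP: missing AE and medication dates "will be imputed in a conservative fashion that will be detailed in the SAP". SAP 6.2.2 repeats the adjective: they "will be imputed in a conservative fashion as in Table 4". Neither document says what the imputation is meant to be conservative for.

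Table 4 has three onset rules:

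- Day missing: "Use the first day of MM to impute the missing date part of the onset date".
- Month and day missing: "Use the first day of YYYY to impute the missing month and date parts of the onset date".
- Whole date missing: no imputation.

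Partial resolution dates go to the last day of the known month or year. The same rules apply to concomitant medications. No rule refers to consent, Day 1 or first injection.

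SAP 4.4.1 makes an AE treatment-emergent "if the AE occurred on or after the date of the first DE-109" treatment in SPRING, up to the last visit. Protocol 12.1.1 commits to reporting both on-study and treatment-emergent AEs. SAP 8.1 then states: "All analysis will focus on on-study AEs given the PRN nature of this study". It meets the treatment-emergent commitment only through a status shown in the AE listings ("The information that whether an AE is treatment emergent or not").

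**The concern.** Taking the earliest start and latest end is conservative for event duration and for counting concomitant use. For a flag that depends on onset falling on or after first injection it is the opposite: it moves events from after exposure to before it.

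Take a first injection on 10 March and an AE that began on 20 March, recorded only as March. Table 4 dates it 1 March, and the listing shows it as not treatment-emergent.

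The study's sole objective is the long-term safety of the 440 µg dose, and the listing flag is the only planned output that places each AE before or after first SPRING exposure. Someone reading the listings would see some post-injection events labelled as pre-injection, under a rule described as conservative. For a completely missing onset there is nothing from which to derive the flag.

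**Working it through.** The documents give no figure to reproduce, so the check applies the two rules to dates.

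**Direction.** Write I for first injection, T for true onset and P for the Table 4 onset. P is never later than T. If the rule gives the flag, then I ≤ P ≤ T, so the AE is truly emergent, provided T is no later than the last visit. Enumeration agrees: of 302,760 pairs with onset 1 to 360 days before injection, none wrongly gains the flag under either rule. The proviso matters: an onset after the last visit, partially dated, could be pulled back into the window. Protocol 12.1.1.2 ends AE recording at Month 12, so that case is outside the plan.

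**Which events lose the flag.** Those with P < I ≤ T: onset in the same known month (or year) as the injection, and the injection not on its first day.

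**Size, by hand.** Assume one injection date for each day of a 365-day year, onset equally likely on each of the 360 days from injection, and every onset partial. That gives 365 × 360 = 131,400 pairs.

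- *Month-only.* A month of L days contributes the sum of (L − d + 1) over injection days d = 2 to L, which is L(L − 1)/2 lost flags. Total: 7 × 465 + 4 × 435 + 378 = 5,373. Share: 5,373/131,400 = 4.1%. Pairs with onset in the injection month number 7 × 496 + 4 × 465 + 406 = 5,738, so 5,373/5,738 = 93.6% of those lose the flag. The rest are injections on the 1st.
- *Year-only.* The sum over d = 2 to 365 of min(366 − d, 360) is 64,980 + 4 × 360 = 66,420. Share: 66,420/131,400 = 50.5%.

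**Size, over the enrolment period.** First injections are taken as uniform from 1 August 2014 (Protocol synopsis, estimated first enrolment in August 2014) to 18 November 2016 (SAP 3.3, enrolment completed), which is 841 dates. Onsets are uniform over the W days from injection:

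| W (days) | Month-only, flag lost | Year-only, flag lost |
|---|---|---|
| 30 | 49.5% | 96.3% |
| 180 | 8.3% | 72.6% |
| 360 | 4.1% | 47.6% |

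Running injection dates on to 18 November 2017 gives 4.1% and 48.5% at 360 days. In the one-year set-up, placing first injection 120 days after Day 1 and keeping onsets within Days 1 to 360 gives 6.2% and 67.0% of truly emergent AEs.

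**Rescue.** SAP 8.7 (Use of Rescue Therapy) summarises time to first rescue from Day 1, and Table 4 also governs medication starts. With Day 1 in place of I, a start truly after Day 1 but partially dated in Day 1's month or year is imputed before Day 1. Over the same 841 dates and 360 days this occurs for 4.1% of month-only starts (on average 10.4 days before Day 1, maximum 30) and 47.6% of year-only starts (average 132 days, maximum 364). The true starts in those cases average 9.5 and 116 days after Day 1.

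**The case against.** The strongest reply is that nothing in the planned AE tables moves. They use on-study AEs. They are also split by whether the subject was injected in SPRING, a subject-level contrast that needs no onset date. Relatedness to drug or procedure is the investigator's entry on the eCRF (SAP 4.4.1.3). This stands. A reader might infer that AE counts or related-event rates are understated; the documents do not support that. It could happen only if on-study status were derived from imputed dates, and the SAP does not say that it is.

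The second reply is that the percentages describe the rule, not the study. This also stands. Protocol 12.1.1.1 and 12.1.1.2 have AEs sought at every contact and recorded with start and end dates, and 15.1 requires source verification, so year-only onsets in a 12-month study should be rare. AEs are also elicited at injection visits, so partial dates are least likely just after an injection, where the 30-day shares apply. Partial dates are still plausible: only 13 of 60 subjects signed consent for the US amendment, which adds the Month 2 to 10 visits, so recall elsewhere may be long.

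The third reply concerns rescue. A reader might infer that negative times will occur. The SAP does not establish this: the Medical Monitor decides before database lock what counts as rescue (SAP 4.5.1), and a negative value depends on how that decision is programmed. A fully dated therapy already running at Day 1 could raise the same problem, but that belongs to the rescue definition, not to Table 4.

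**Conclusion.** The point holds for the treatment-emergent flag. Followed literally, Table 4 mislabels post-injection AEs whose known month or year is that of the first injection, and for AEs between consent and last visit the error is one-directional. Completely missing onsets are left without a rule.

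The consequence is limited to the listing annotation. It is worth correcting because that annotation is how the protocol's commitment on treatment-emergent AEs is met, and because a rule called conservative is anti-conservative for it.

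About 4% of month-only and 48% of year-only onsets would lose the flag over 360 days, assuming uniform injection dates and onsets. These are shares of partially dated AEs, not of all AEs. The count of such AEs is not in the documents, so no expected number of wrong flags can be given.

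The rescue point is secondary: a negative time is possible, not certain. The summary covers rescued subjects only, not all 60, so a single such value could weigh on its mean and minimum.

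**What to change.** In SAP 6.2.2/Table 4 and the ADaM specification:

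1. Keep the Table 4 dates for duration, but derive the treatment-emergent flag separately. In subjects injected in SPRING, flag a partly or completely missing onset as treatment-emergent unless the known date parts show onset before first SPRING injection, or the resolution date as imputed by Table 4 precedes that injection. Subjects never injected have no treatment-emergent AEs.
2. State that every AE on the AE eCRF stays on-study whatever its imputed date.
3. For time to first rescue, do not let the imputed start of a therapy classified as rescue and started during SPRING precede Day 1. Mark such times as imputed in the listing.

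Step 1 loses no true flags: a truly emergent AE never has known date parts earlier than the injection's, and its Table 4 resolution date is never earlier than its true one.

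The cost is a few lines of text and no new data. The remaining error in step 1 runs the cautious way: some AEs between consent and first injection will be flagged emergent. For a 30-day gap this is about 49% of month-only and 96% of year-only AEs in that interval; for 60 days, about 24% and 91 to 93%. Subjects injected on Day 1 have little or no such interval. A completely missing onset is flagged unless its resolution date rules it out, and the cost of that has not been quantified.

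Step 3 removes impossible values but still biases the time low, since the affected true starts average 9.5 days (month-only) or 116 days (year-only) after Day 1 under the assumptions above. That is why the imputed times should be marked.

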## 6.3. Multi-Center Studies

This is a multi-center study enrolling subjects from sites in multiple countries, including the US, India, and Europe.

## 6.4. Multiple Comparisons / Multiplicity

Multiplicity adjustment is not applicable to the descriptive summaries of this study.

## 6.5. Interim Analysis

No formal interim analysis is planned for this study.

## 7. SUMMARY OF STUDY POPULATION DATA

### 7.1. Subject Disposition

The subject disposition for all enrolled subjects will be tabulated by Safety population. Safety population will be further tabulated by subjects who completed study exit assessment and Month 12 Visit completers. Non-completers at Month 12 will be tabulated by the primary discontinuation reason and will be listed by subject ID. Days to premature discontinuation will also be summarized.

The subject enrollment will be summarized by geographic region and country, if applicable.

### 7.2. Demographics and Baseline Characteristics

Subject demographics and baseline characteristics will be descriptively summarized for the Safety Population. Subject demographics collected under Protocol 32-009 include age at entry, gender and geographic region. Race and ethnicity for the Safety Population will be carried over from the SAKURA program.

For baseline characteristics, the baseline scores of the following variables will be summarized:

- Baseline VH score of study eye
- Anatomic location of uveitis of study eye (intermediate, posterior or panuveitis)
- Presence of cataract in the study eye (Phakic lens only) (yes or no)
- Baseline BCVA of study eye
- Use of systemic corticosteroid
- Rescued in SAKURA study
- Entered open-label period in SAKURA study

Other baseline characteristic variables may be summarized as suggested by the data.

### 7.3. Medical and Surgical History

The medical history events will be coded using the MedDRA Version 16.0 and summarized for the Safety population.

Subjects reporting any medical history events will be tabulated by System Organ Class (SOC) and preferred term specified in MedDRA. In addition, the following subsets of medical history events will be tabulated:

- SOC *Eye Disorders* medical events in study eye by Preferred Term and Lowest Level Term
- Medical events ongoing at baseline by SOC and Preferred Term

- SOC Eye Disorders medical events ongoing at baseline in study eye by Preferred Term and Lowest Level Term

Any subject with more than one medical and/or surgical term within the same SOC (or mapped to the same preferred term) will be counted only once for that SOC (or preferred term).

#### **7.4. Protocol Deviations**

Protocol deviation(s) will be listed by geographic region (US, EMEA, or India) and subject. Major protocol deviations will be tabulated by deviation category.

#### **7.5. Prior and Concomitant Medications**

For Safety subjects, all non-study medications will be tabulated by ATC level and WHO-DDE preferred drug name. A subject will be counted at most once for each non-study medication, even if the subject received the same medication on multiple occasions. Details of those non-study medication usages will be listed including subject information, start and end date of the medication, unit, dose and frequency.

#### **7.6. Treatment Exposure**

The extent of exposure to DE-109 (440 µg) in the SPRING study will be assessed by the number of DE-109 injections (0, 1, 2, 3, 4, 5, or 6) together with days on treatment (<60, ≥60 and <120, ≥120 and <180, ≥180 and <240, ≥240 and <300, or ≥300).

### **8. SAFETY ANALYSES**

Safety measures collected in this extension study include:

- On-Study AEs
- VH
- BCVA
- IOP
- Indirect ophthalmoscopy
- Treatment exposure
- Use of rescue therapy
- Slit-lamp Biomicroscopy
- Central Retinal Thickness

Unless specified otherwise, safety measures collected from both eyes will be summarized for study eyes and fellow eyes separately.

#### **8.1. Adverse Event**

All AE(s) will be coded by MedDRA 16.0, 2013. All analysis will focus on on-study AEs given the PRN nature of this study. The information that whether an AE is treatment emergent or not

will be provided in all the AE related listings. All AE tables will be summarized by last dose received in SAKURA study, received injection or not in SPRING study, and overall.

Besides the overall summary of AEs, subjects with any AE(s) will be tabulated by SOC, preferred term, and maximum severity. A subject who experienced multiple AEs within a SOC or preferred term will be counted only once for that SOC or preferred term. SAEs, SARs, Serious SARs, study-medication related AEs, and injection-procedure related AEs will be tabulated similarly.

Ocular AEs, ocular SARs, serious ocular AEs, and serious ocular SARs will be summarized. Any ocular AE that occurred simultaneously to both eyes will be counted once for both the study eye and the fellow eye.

Sight-threatening AEs will be summarized by type of event specified in [Section 4.4.1.2.1](#).

Eye disorders AEs may be tabulated using lowest level term and preferred term to provide more detailed information.

Non-ocular AEs and serious non ocular AEs will be presented by SOC and preferred term.

All AEs reported during the study will be listed. SAEs, SARs, Ocular AEs, study-medication related AEs, injection-procedure related AEs, AEs leading to death, AEs leading to discontinuation, sight-threatening AEs, and ESIs, if any, will be listed separately.

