## 12. ASSESSMENT OF SAFETY

### 12.1. Adverse Events, Serious Adverse Events and Events of Special Interest

#### 12.1.1. Definition of Adverse Events

An AE is any untoward medical occurrence in a subject administered a pharmaceutical product and which does not necessarily have a causal relationship with study drug. An AE therefore can be an unintended sign (including an abnormal laboratory finding), symptom, or disease temporally associated with the use of a medicinal (investigational) product, whether or not related to the medicinal (investigational) product.

In clinical studies, an undesirable medical condition occurring at any time, including baseline or wash-out period, may be recorded as an AE even if no study drug has been administered.

Any significant change in a subject's condition from baseline, regardless of causality, is to be considered an AE, unless the change is determined to be a continuation of a pre-existing condition that is documented in the subject's medical history. However, a clinically significant worsening in severity, intensity, or frequency of a pre-existing condition may indicate an AE.

Lack of efficacy of the study drug for the condition being investigated is not considered an AE unless a clinically significant change is assessed by the Investigator. In addition, any elective surgical procedure scheduled or planned prior to study entry is not considered an AE and the underlying diagnosis for which surgery is to be performed should be captured in the medical history as a pre-existing condition.

For this protocol, an AE is any *on-study* untoward medical occurrence (e.g. sign, symptom, disease, syndrome, intercurrent illness) that occurs in a study subject, regardless of the suspected cause and regardless of timing of DE-109 (440 µg) administration. An on-study AE can occur anytime after the date of informed consent through the last study visit. An AE will be considered as *treatment-emergent* if the AE occurred on or after the date of the first DE-109 (440 µg) treatment up to the last study visit. Treatment-emergent AEs are a subset of on-study AEs. Both on-study and treatment-emergent AEs will be reported.

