## 14. STATISTICAL METHODS

### 14.1. General Considerations

This protocol is implemented to evaluate the long-term safety of treatment with DE-109 (440 µg) in subjects with non-infectious uveitis of the posterior segment of the eye among those subjects who received at least two treatments of DE-109 during the first five months of the SAKURA program and received clinical benefit, as determined by the Investigator. The minimum time lag from last injection during the SAKURA program to entry into the current protocol is 60 days.

Study visits for assessment are scheduled at Day 1 and Month 12. At the discretion of the investigator, dosing of DE-109 (440 µg) may take place at Day 1 or at any Post-Baseline PRN Treatment Visit prior to the Month 12 assessment visit.

The descriptive statistics will include number of observations (n), mean, standard deviation, minimum, and maximum for continuous parameter and frequency (n) and percent (%) for categorical parameters. No statistical hypothesis testing will be conducted on any parameter.

Details about the statistical analyses for this study will be provided in the statistical analysis plan (SAP).

All data manipulations and descriptive summaries will be implemented using SAS®, Version 9.1.3 or later.

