### **8.6. Treatment Exposure**

The exposure to DE-109 will be evaluated by descriptive summaries of number of injections during the study, time to first injection, and study days on the drug.

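### The SAP plans no table of treatment-emergent adverse events, although the protocol says they will be reported and safety of treatment with 440 µg is the only objective

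*SAP*

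**What the plan says.** Protocol 12.1.1 defines two sets of adverse events, on-study and treatment-emergent, the second a subset of the first, and commits to both: "Both on-study and treatment-emergent AEs will be reported".

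SAP 4.4.1 repeats the definition. An event is treatment-emergent if it occurred "on or after the date of the first DE-109 (440 µg) treatment in Spring Study up to the last study visit".

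SAP 8.1 then sets the scope of the outputs: "All analysis will focus on on-study AEs given the PRN nature of this study". Whether an event is treatment-emergent "will be provided in all the AE related listings"; no table is named for it. The table layout is: "All AE tables will be summarized by last dose received in SAKURA study, received injection or not in SPRING study, and overall".

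Three other provisions bear on the point:

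- SAP 5.1 includes subjects in the Safety population "regardless of receiving an injection of DE-109 (440 µg) or not in this study".
- Protocol 14.1 says that dosing "may take place at Day 1 or at any Post-Baseline PRN Treatment Visit prior to the Month 12 assessment visit".
- SAP 8.6 plans to summarize "number of injections during the study, time to first injection, and study days on the drug".

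**The concern.** The sole objective (Protocol 6, SAP 2) is the long-term safety of treatment with DE-109 440 µg. The most direct summary is the share of subjects with an event once they had received that dose in this study, and the SAP does not tabulate it.

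A reader looking for that figure will probably use the column for subjects injected in SPRING. With PRN dosing, that column can mix events before and after the first SPRING injection. An event before it still follows DE-109 exposure, because Protocol 8.1 requires at least two SAKURA injections. However, the SAKURA dose may have been 44 or 880 µg (Protocol 5) rather than 440 µg.

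Exposure and events would also run on different clocks. SAP 4.1.3 starts days on treatment at the first SPRING injection, and SAP 7.6 tabulates exposure on that basis, while the AE tables count from consent.

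**Working it through.** **Step 1. Does any planned table apply the treatment-emergent window?** The AE outputs in SAP 8.1, one by one:

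- The tables by SOC, preferred term and maximum severity use on-study events.
- The tables of serious, ocular and non-ocular events name no onset restriction.
- The study-medication-related, injection-procedure-related and suspected-reaction tables select on investigator causality (SAP 4.4.1.3) in an open-label study. They are not all-cause.
- The split by SPRING injection is a yes/no attribute of the subject, with no onset rule.
- The listings carry the treatment-emergent item, but give no incidence and no denominator.

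None gives all-cause incidence from the first SPRING injection.

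**Step 2. Can the injected column differ from treatment-emergent incidence?** It is the same only if no injected subject is counted solely because of an event before the first injection. Protocol 14.1 allows a first injection after Day 1, Protocol 9.3 requires no injection at any visit, SAP 7.6 includes a category of zero injections, and SAP 8.6 plans to summarize time to first injection. The SAP therefore does not assume dosing on Day 1.

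**Step 3. How large could the difference be?** The plan states no AE rate, power or precision, so there is no figure to reproduce. What follows is illustration.

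Inputs: N = 60 (SAP 3.3) and 360 days of follow-up (Month 12 is Day 360). Assumed: on-study incidence p over 360 days, a constant hazard, and one common delay of d days to first injection.

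Incidence on or after first injection = 1 − (1 − p)^((360 − d)/360)

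Example with p = 0.30 and d = 120: 1 − 0.70^(240/360) = 0.212.

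| On-study incidence p | d = 0 | d = 60 | d = 120 | d = 180 |
|---|---|---|---|---|
| 10% | 10% | 8.4% | 6.8% | 5.1% |
| 30% | 30% | 25.7% | 21.2% | 16.3% |
| 60% | 60% | 53.4% | 45.7% | 36.8% |

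If all 60 subjects were injected with that delay (an upper bound), the number in the injected column whose only events came before injection is 60 × (p − incidence after injection). For p = 0.30 and d = 120 this is 60 × (0.300 − 0.212) = 5.3.

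| p | d = 60 | d = 120 | d = 180 |
|---|---|---|---|
| 10% | 1.0 | 1.9 | 2.9 |
| 30% | 2.6 | 5.3 | 8.2 |

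**Step 4. A milder case.** Let a share f of injected subjects start late, at month t, and the rest on Day 1. Then incidence after injection = (1 − f)p + f[1 − (1 − p)^((12 − t)/12)]. With p = 30%, 50% or 70% and t = 2, 4 or 6, the gap is 0 points for f = 0, 1.1 to 6.2 points for f = 25%, and 2.1 to 12.4 points for f = 50%. For example, p = 50%, f = 50% and t = 4 give 50.0% on-study against 43.5% after injection.

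**Step 5. Is the listing item itself safe?** SAP Table 4 moves a partial onset date to the first day of the known month or year. An event in the month (or year) of first injection with the day (or month and day) missing is then dated before the injection, unless the injection was on that first day. It loses treatment-emergent status even if it began afterwards, and Table 4 does not compare the imputed date with the injection date.

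**The case against.** The SAP's choice is open and reasoned. On-study events contain every treatment-emergent event, so nothing is lost, and Protocol 14.2 makes the whole Safety population the population for safety summaries. The protocol promises that both sets will be reported, not tabulated; Protocol 14.6 lists the AE tables without naming a treatment-emergent one, and a listing that carries the item is arguably a report. SAP 8.1 also mentions an overall AE summary whose rows are not described. The SAP applies to US Amendment 01, whereas the supplied protocol lacks that amendment's Month 2 to 10 visits, so whether the amendment keeps the reporting sentence cannot be checked. Finally, a treatment-emergent proportion mixes post-injection windows of different lengths, so late starters have lower values by construction.

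Much of this stands, and it limits the severity. Nothing shows that any first injection was late. The counts could be rebuilt by hand for 60 subjects. Under a constant hazard the gap in Step 3 reflects a shorter window, not a different rate. On the amendment, only 13 of the 60 subjects signed its consent (SAP 3.3), which leaves 60 − 13 = 47 who did not.

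The gap remains. A listing gives no incidence, no denominator and no summary by SOC or preferred term, while AE incidence is the first analysis parameter in Protocol 14.1.1. PRN dosing is a good reason to keep the on-study tables, but it is also what makes the two sets differ, so it does not justify leaving out the second.

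**Conclusion.** The concern holds. The protocol commits to reporting treatment-emergent events; the SAP defines them and then plans no table of them. The injected column is not a substitute, because it has no onset rule.

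The size cannot be known from the documents. It is zero if all first injections are on Day 1. Under the assumptions in the working, it ranges from about 1 point (30% incidence, a quarter of injected subjects starting two months late) to 13.7 points (30% on-study against 16.3%, all starting 180 days late), and it is larger at higher incidence. These figures rest on an assumed rate, a constant hazard and assumed delays; they are not findings about this trial. No hypothesis is tested, so the consequence is confined to descriptive reporting. It should be fixed because it concerns the study's only objective and the remedy is cheap.

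**What to change.** Amend SAP 8.1 as follows:

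1. Keep the on-study AE tables in the Safety population.
2. Add treatment-emergent tables using the SAP 4.4.1 definition: an overall summary; SOC, preferred term and maximum severity; serious; ocular by eye; and related events. The denominator is subjects with at least one SPRING injection, and the SAP should define that set.
3. Show events with onset before the first SPRING injection separately.
4. State how an event is classed when its onset date is partial and falls in the month or year of first injection. One workable rule is to count it as treatment-emergent unless the recorded date parts or the resolution date show that it began earlier. The rule should also cover a completely missing onset date, which Table 4 does not impute.
5. Optionally, add a rate per person-time from first SPRING injection to exit, using days on treatment as defined in SAP 4.1.3. This is the one item that deals with unequal windows after injection.

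The cost is low: SAP wording and additional tables. The treatment-emergent item and the injection dates already exist, so no new data are needed. The drawback is a larger table set with small cells in 60 subjects, given the existing split by last SAKURA dose.
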